4. BACKGROUND

Current practice of preoperative evaluation does not consider the intrinsic capacity of older adults to tolerate stress related to surgery. Frailty is a measure of intrinsic capacity.⁴ Individuals with frailty have decreased physiologic reserve to tolerate stressors,⁵ and thus they are more likely to experience poor surgical outcomes, such as complications, mortality, readmission, functional decline, and discharge to an institution.^{6,7} While it is a reliable measure of surgical risk, frailty is not part of the preoperative assessment of older adults. Frailty assessment within the context of a comprehensive geriatric assessment—a multi-domain assessment of medical history, functional status, cognition, mood, physical performance, and nutritional status⁸—provides not only risk stratification but also opportunities to optimize modifiable risk factors to improve surgical outcomes.

Optimizing risk factors before surgery may improve outcomes. Interventions to increase reserve through physical activity and nutritional interventions before surgery are biologically plausible ways to improve surgical outcomes, but they are not routinely done in practice. To date, studies on prehabilitation have mostly been on gastrointestinal,⁹⁻¹³ cardiothoracic,^{10,14} and orthopedic surgeries¹⁵ with physical activity and nutrition as single or dual interventions.^{9-12,14} There are only a small number of RCTs on a multicomponent prehabilitation (≥ 3 interventions).¹⁶⁻²¹ Some studies have shown that prehabilitation may decrease length of stay and postoperative complications, and improve function, while others did not show benefits.^{9,11,12,14,22,23} Systematic reviews concluded insufficient evidence for prehabilitation for clinical use due to significant limitations of studies, including small sample sizes,^{11,13,15,24,25} increased risk of bias (e.g., single-arm studies),^{9-11,14,23,26} and lack of attention to adherence.^{13,14,21,24,26} Little is known about facilitators of and barriers to adhering to prehabilitation interventions, particularly among frail patients.^{27,28} Moreover, evidence as to which patients will most benefit from prehabilitation^{10,29} and the effect of prehabilitation on patient-centered outcomes¹⁴ are lacking.

The efficacy and potential mechanisms of interventions are supported by evidence (**Table 1**). Short duration (3-4 week) intensive exercise and protein-focused nutrition programs have also previously been shown to improve physical measures^{30,31} and outcomes^{18,19,32-34}; however, a robust RCT of a multi-component prehabilitation program addressing the aforementioned gaps is still needed.

[figure not shown]
Table 1. Evidence and potential mechanisms for multi-component prehabilitation program

Intervention	Evidence	Mechanisms
Exercise	Meta-analysis of RCTs (Lau 2020)	
 ↑ Anabolic effect on protein synthesis ↓ Catabolic effect of inflammation on muscles
Nutrition	Meta-analysis of RCTs (Gillis 2018)	
 Overcome age-related anabolic resistance Meet increased need for protein due to inflammation
Mindfulness meditation	RCT (Hanley 2021) & single-arm study (Chavez 2020)	
 Improve sleep by ↑ melatonin, ↓ GABA Reduce pain and anxiety by thalamic deactivation and orbito-frontal activation; ↓ pain-related afferent processing; resetting expectations Improve cognition by ↑ alpha-band power; ↑ BDNF; ↑ network connectivity
Cognitive behavioral strategies	RCT (Latham 2014)	
 Improve adherence to the intervention components as an adjunct intervention

BDRF, brain-derived neurotrophic factor; ONS, oral nutritional supplement; PROMIS, Patient-Reported Outcomes Measurement Information System

To accomplish this, we are planning to conduct an RCT of a multi-component prehabilitation program versus usual care on patient-centered outcomes in older adults undergoing major surgery (**Figure 1**).

Figure 1. Conceptual model for an RCT of prehabilitation program. Abbreviation: CGA, comprehensive geriatric assessment.

In this future RCT, we will identify candidates for prehabilitation based on the patient's frailty level, which represents the physiologic reserve to tolerate stress from surgery and hospitalization. We will provide a multicomponent intervention which not only addresses the body but also the neurobehavioral aspect of a frail patient, given the link between frailty and cognition.²⁸ We will measure patient-centered outcomes using validated Patient-Reported Outcomes Measurement Information System (PROMIS) measures.²⁹ Therefore, we propose this pilot study to assess the feasibility of key steps of this ideal RCT and refine a multicomponent prehabilitation protocol to ensure its feasibility and adherence.

5. STUDY POPULATION

We will review schedules to identify patients who meet the following inclusion (5.1) and exclusion criteria (5.2). A trained research assistant will perform preoperative geriatric assessment—which consists of 1) medical history (automated in EHR), 2) self-reported functional status (a questionnaire of 22 daily activities and physical tasks), 3) tests of cognitive function (Mini-Cog or MoCA test) and physical function (gait speed, chair stands, and grip strength), and 4) nutritional status (automated in EHR)—and calculate a frailty index using our EHR calculator. For eligible patients, we will explain the purpose of our study to the patients and their surgeon and ask whether they are willing to participate in 3 to 4 weeks of prehabilitation. Remote or e-consent will be obtained. Screening of potential participants will take place during the surgeon’s office visit. The assessment of eligibility will take place by telephone. Our target enrollment is 30 patients (2 patients per week for 15 weeks). See the detailed inclusion and exclusion criteria provided below:

5.1 Inclusion Criteria:

- Patient is ≥ 70 years
- Patient is ≥ 65 years old AND high risks per surgeon’s clinical judgement
- Patient is scheduled to have a gastrointestinal, gynecological oncologic, urologic, and cardiovascular procedure
- Patient provides an informed e-consent or remote consent

5.2 Exclusion Criteria:

- Surgery is scheduled less than 21 days from the expected start date of the prehabilitation intervention
- Patient is considered an inappropriate candidate per the surgeon’s assessment.
- Non-English speaking
- Patient has a major cognitive impairment, which will be defined as telephone Montreal Cognitive Assessment (MoCA) <18 or Brief Capacity Assessment Questionnaire
- Patients with chronic kidney disease stage 3 or higher will be excluded from receiving protein supplement of the prehabilitation intervention.

[figure not shown]
6. ENROLLMENT

As stated above, patients who are scheduled to undergo a gastrointestinal, gynecological oncologic, and urologic surgery, meet inclusion criteria, and have approval from their surgeon to participate will be contacted by a study clinician who will assess eligibility, including a telephone-based preoperative frailty assessment (only patients with frailty will be eligible). This assessment includes the following domains:

- Medical history
- Self-reported functional status (activities of daily living [ADL], instrumental activities of daily living [IADL], and physical tasks without another person's help)
- Tests of cognitive function (Telephone MoCA)
- Nutritional status (BMI and self-reported weight loss)

Most of these assessments are already available or routinely collected and entered in BIDMC Online Medical Record (OMR). The study clinician will verify the existing information in OMR with the patient and fill in any missing information if needed. The OMR frailty index calculator calculates the frailty index based on information available in OMR (Figure 2). The index ranges from 0 to 1; frailty is defined as ≥ 0.25 .

Figure 2. Example report of OMR frailty index calculator and assessment report. The frailty index calculator (A) will use the latest information available in OMR to calculate a deficit-accumulation frailty index. The report shows the assessment domain-specific impairment and comparison of the frailty index against a reference population of Medicare beneficiaries.

6.1 Baseline Assessment

Once informed e-consent or remote consent is signed, trained research personnel will administer additional measurements that are not collected as part of preoperative assessment. These measurements (provided below) may be conducted 1) during the telephone call during which informed consent is obtained; 2) during a separate call (if

requested by the patient or caregiver); 3) email survey; 4) during an in-person physical therapy session (for gait speed, chair stands, and handgrip strength); or 5) a combination of these modalities.

- Usual walking speed from 4-meter walk (if not already measured)
- Time to complete 5 chair stands (if not already measured)
- Dominant handgrip strength: average of 3 measurements (if not already measured)
- 3-day diet recall (done by telephone)
- PROMIS Profile CAT v1.0 is a 29-item, computer adaptive, patient-reported outcome measure of social roles/activities, anxiety, depression, fatigue, pain interference/intensity, physical function, and sleep disturbance domains (may be done by telephone or email)
- PROMIS v2.0 Cognition CAT is a 12-item, computer adaptive, patient-reported outcome measure of cognitive function domain (may be done by telephone)

PROMIS (available at <https://www.healthmeasures.net/index.php>) is a publicly available, validated system of highly reliable, precise measures of patient-reported health status for physical, mental, and social well-being for general population as well as people with chronic conditions. It is designed to enhance communications between clinicians and patients in diverse clinical and research settings. Computer adaptive test (CAT) allows accurate assessment with a limited number of questions from the PROMIS item bank, thereby reducing participant burden.

6.2 Medical Record Review:

Trained research personnel will obtain the following data from the OMR and record them in REDCap database:

- Demographic information: age, sex, race, ethnicity
- Chronic comorbidities
- Self-reported functional status: ADL, IADL, physical tasks by Nagi and Rosow-Breslau
- Cognitive function: telephone MOCA
- Physical function: gait speed, dominant handgrip strength, and chair stands
- Nutritional status: height, weight, BMI, weight loss in the past year, serum albumin level

7. STUDY INTERVENTION

All participants will be enrolled in a prehabilitation program that will start 3-4 weeks prior to the date of scheduled surgery. The intervention will target three principal components (physical activity, nutrition, and meditation) and deliver cognitive behavioral interventions

(Table 3). Each intervention has 1) instructional or training components, delivered by our study team, and 2) self-directed components.

Table 3. Multicomponent prehabilitation program and measures of feasibility and adherence for each component

Target	Intervention	Measures of Feasibility or Adherence
Exercise: Increase muscle function	
 • Physical therapy (home, in-person, hybrid or virtual) 
 • By physical therapists • Average two 1-hour individual sessions per week (delivered in patient's home, in-person center, hybrid, or virtual) • Goal: 6-8 total PT sessions • Endurance, strengthening, flexibility • Self-directed exercise 
 • Goal: 30 mins/day x 4 days per week 	
 • Number of sessions delivered (feasibility) 
 • Number of days with ≥ 30 min exercise per self-report diary • Step count from a wearable activity tracker (Fitbit Fitness tracker): provision of weekly feedback based on step count • Change in 5-chair stands and grip strength pre- and post- intervention
Nutrition: Preserve lean body mass (Patients with CKD will be excluded)	
 • Nutrition counseling 
 • By registered dietitian • Average one 1-hour group session per week • Goal: 3-4 total nutrition education sessions • Self-directed protein consumption 
 • Goal: 1-2 ONS (20 gram)/day x 4 days per week 	
 • Number of sessions delivered (feasibility) 
 • Number of ONS consumed per self-report • Change in protein intake per 3-day dietary recall pre- and post- intervention • Change in quadriceps thickness by ultrasound pre- and post- intervention
Meditation: Increase cognitive resilience	
 • Mindfulness meditation 
 • By meditation teacher • Average one 1-hour group session per week • Goal: 3-4 total guided meditation sessions • Self-directed meditation 
 • Goal: 12 mins/day 	
 • Number of sessions delivered (feasibility) 
 • Number of days with ≥ 12 min meditation per diary
Cognitive behavioral interventions: Improve adherence to the above 3 core interventions	
 • Cognitive behavioral interventions 
 • By research staff certified in cognitive behavioral therapeutic techniques • Education about frailty, discussion about barriers, writing down individualized goals, and weekly progress review • Average one 30-min individual session per week • Goal: 3-4 total cognitive behavioral sessions 	
 • Number of sessions delivered (feasibility)

Abbreviation: CKD, chronic kidney disease; ONS, oral nutritional supplement; PROMIS, Patient-Reported Outcomes Measurement Information System. * Participants living within a 20-mile radius from HSL will be offered home in-person, center based, or hybrid physical therapy.

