2. OVERVIEW

The purpose of this feasibility pilot study is to understand how a prehabilitation program for older adults with frailty can best be optimized to prepare at-risk patients for major surgery. As such, our program interventions target major risk factors that are modifiable yet rarely addressed in the pre-surgery period (physical function, nutrition, pain, sleep, anxiety, and cognition). We also aim to determine how these interventions can best be delivered for optimal participation.

Participants will receive 3 to 4 weeks of exercise training with a physical therapist, nutrition education with a registered dietitian, meditation with an experienced meditation teacher, and cognitive behavioral intervention to discuss goals, facilitators and barriers to program adherence with the goal to enhance motivation and promote self-efficacy. Two (2) follow-up assessments will additionally be performed at days 30 and 90. Further details of the intervention are provided below:

- Exercise training with home/virtual/in-center physical therapy will take place on average twice a week for 1 hour per session over 3-4 weeks. The participant will be encouraged to exercise on their own for 30 minutes per day for 4 or more days a week and track exercise in a diary (number of minutes achieved per day). They will also be asked to wear a physical activity tracking device (Fitbit Fitness tracker) to measure daily number of steps, active minutes, and heart rate. This device will also remind the participant to get up and move throughout the day.
- Nutrition class with a licensed nutritionist (registered dietitian) will take place on average once a week for 1 hour per session over 3-4 weeks. The participant will also be asked to drink/consume 1 high calorie, high protein nutritional supplement per day which will be provided to them by the study. They will be asked to write down their approximate daily food intake in a diary (3 days/week) – this will be an informal accounting of their intake with the primary focus being on protein-containing food items. This information will be used to measure their protein intake during their participation in the study.
- Meditation with a yoga/meditation teacher will take place once a week for 1 hour per session over 3-4 weeks. The participant will also be asked to practice meditation on their own for at least 12 minutes each day and track in a diary (number of minutes achieved each day).

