7.1 Component 1: Exercise

The instructional part will be delivered via average twice weekly, one-hour, in-person home, center-based, or virtual (via HSL's Zoom video-conferencing software) physical therapy sessions, depending on the patient's preference, familiarity with technology, availability of transportation, and other contingencies (e.g., COVID-19 based restrictions, incremental weather). Evidence suggests that virtual sessions offer similar benefits to in-person home sessions³⁰ or in-clinic sessions.³¹ Although a twice-weekly schedule is aimed, the schedule will be adjusted flexibly to deliver a total of 6-8 sessions.

Exercises targeting flexibility, strength, and endurance will be adopted mainly, though not exclusively, from the NIA Go4Life guide (<https://go4life.nia.nih.gov/>). Sample exercises are shown in **Table 4**.

Before each in-person or virtual physical therapy session, the study physical therapist will review safe areas for exercise, safety techniques and warning signs (such as chest pain or pressure, severe dyspnea, left shoulder or arm pain, indigestion, heart palpitations, lightheadedness, dizziness, and headache). Participants will begin at a low level of effort and incrementally increase exercise intensity according to the therapist's guidance. For virtual sessions and self-directed exercise, we will ask caregivers, family members, or home health personnel to provide supervision for safety and development of adverse events, whenever possible. During the in-person session, blood pressure, heart rate, and blood oxygen level will be monitored by the physical therapist.

The self-directed part will include self-directed exercise (any types of exercise) at least 30 minutes per day for 4 or more days per week. Step count data from a wearable device (Fitbit Fitness Tracker) will monitor progress and provide feedback, which improves adherence in older adults. Fitbit Fitness tracker will either be provided at the pre-admission testing visit or mailed to the patient's home.

Table 4. Sample exercises for flexibility, strength, and endurance (source: Go4Life)

Flexibility (stretching)	Strength	Endurance

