7.2 Component 2: Nutrition

The instructional part will be delivered in once-weekly (on average), one-hour, virtual group sessions (via HSL Zoom software) by co-investigator/registered dietitian, [name], (the virtual sessions will be offered at three different days/times to accommodate participants' schedules). This nutrition counseling will focus on optimal protein intake (1.2 gram per kg of body weight) for lean body mass preservation (from food sources and oral nutritional supplements). Sessions will focus on nutrition for muscle gain and lean body mass preservation with topics including:

- *Session 1:* Good sources of protein and total needs (1.2 grams x weight in kg)
- *Session 2:* Protein intake timing: rule 15/30 (at least 15 grams within 30 minutes of exercise)

- Session 3: Protein for muscle gain
- Session 4: Tips to increase protein intake

The self-directed part will include consumption of oral nutritional supplements (20-30 grams of protein/day and between 150-350 calories/day, such as Think! High Protein Bar (20 grams protein, 22 grams carbohydrate, 150 calories) or Ensure Enlive (20 grams protein, 45 grams carbohydrate, 350 calories) , which will be provided by our study team. Oral nutrition supplements (ONS) will be ordered directly from the product manufacturer in bulk and mailed to the patient's home by a research assistant. Due to ongoing supply chain shortages of popular nutrition supplements, we have identified multiple that meet the above macronutrient parameters. All supplements will be purchased in bulk for each participant with enough to last the entirety of the study. Supplements will not be changed unless the patient reports an adverse event such as GI distress (please see section *B5* for more detailed information). Protein supplements are shelf-stable and can be stored at room temperature until use by date when unopened. Once opened, product should be refrigerated within 4 hours. After opening, any remaining product should be discarded within 48 hours – though patients will be encouraged to consume product in its entirety within 24 hours per study protocol.

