8.2 Secondary Outcomes

For *secondary outcomes*, we will measure the following:

- Change in 5-chair stand test (time)
 - Measurement: time to complete 5 chair stands (seconds), post-prehabilitation minus pre-prehabilitation
 - Range: -60 to 60 seconds (higher values indicate worsening performance)
- Change in dominant handgrip strength (kg)
 - Measurement: average of 3 measurements of dominant handgrip strength, post-prehabilitation minus pre-prehabilitation
 - Range: -50 to 50 kg (higher values indicate improved performance)
- Change in protein intake (grams)
 - Measurement: 3-day average protein intake from dietary recall, post-prehabilitation minus pre-prehabilitation
 - Range: -100 to 100 grams (higher values indicate greater intake)
- Adherence to exercise
 - Measurement: proportion of days with ≥ 30 minutes of exercise out of 21-28 days per self-report
 - Range: 0-100% (higher values indicate better adherence)
- Adherence to protein intake
 - Measurement: proportion of oral nutritional supplement consumed over the total number of supplements provided per self-report

- Range: 0-100% (higher values indicate better adherence)
- Adherence to meditation
 - Measurement: proportion of days with ≥ 12 minutes of meditation out of 21-28 days per self-report
 - Range: 0-100% (higher values indicate better adherence)
- Adverse events
 - Measurement: proportion of patients who experience any adverse events per self-report
 - Range: 0-100% (higher values indicate more adverse events)

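### Table 3's supplement goal conflicts with the one-a-day instruction in Section 2, and protein adherence in 8.2 is divided by a supply whose count is not stated

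*Combined protocol and SAP*

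**What the plan says.** Four places in the combined protocol and SAP bear on the dose.

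- Section 2 (Overview): each participant is asked to "drink/consume 1 high calorie, high protein nutritional supplement per day", and the same sentence says that the study supplies it.
- Section 7, Table 3, nutrition row: "Goal: 1-2 ONS (20 gram)/day x 4 days per week".
- Section 7.2: the self-directed part is "consumption of oral nutritional supplements (20-30 grams of protein/day and between 150-350 calories/day", with a bar (20 g protein, 150 calories) and a shake (20 g protein, 350 calories) as examples.
- Section 12.2: participants given the shake are limited to one supplement a day. If gastrointestinal distress persists, they move to a bar or powder.

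On supply, Section 7.2 says: "All supplements will be purchased in bulk for each participant with enough to last the entirety of the study". No section gives a number of units.

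On measurement, Section 8.2 defines adherence to protein intake as the "proportion of oral nutritional supplement consumed over the total number of supplements provided per self-report", with a range of 0-100%. The exercise measure beside it counts days with enough "minutes of exercise out of 21-28 days per self-report", and the meditation measure is built the same way. Section 12.4 uses a different protein criterion for progression to the RCT: intake on at least 4 days a week.

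On kidney disease, Section 5.2 says: "Patients with chronic kidney disease stage 3 or higher will be excluded from receiving protein supplement of the prehabilitation intervention". Table 3's nutrition row and Section 7.2 repeat that exclusion.

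**The concern.** A supplement dose should read the same wherever it appears, because staff take participant instructions from it. Here a coordinator working from Table 3 could tell someone to take two units on four days, while one working from Section 2 would say one unit every day. For shake users the difference touches a protective measure: the one-a-day limit sits in the section on protection against risks, beside the steps for gastrointestinal distress.

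The second issue is what the 8.2 percentage means. Units provided can be counted, so the ratio can be computed. But it depends on how much was shipped as well as on how much was taken, so two participants with the same intake can score differently. Adherence belongs to Aim 1, and the pilot is meant to hand a workable dose and a readable adherence figure to the RCT.

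**Working it through.** The plan reports no number of units supplied and no expected adherence, so there is no figure to reproduce. The check is direct arithmetic.

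**Step 1. Dose.** Units per week = units per day × days per week; grams = units × 20.

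| Source | Units per week | Protein per week | Protein on a supplement day |
|---|---|---|---|
| Section 2 | 1 × 7 = 7 | 7 × 20 = 140 g | 20 g |
| Table 3, lower | 1 × 4 = 4 | 4 × 20 = 80 g | 20 g |
| Table 3, upper | 2 × 4 = 8 | 8 × 20 = 160 g | 2 × 20 = 40 g |
| Section 7.2 | not stated | 7 × 20 = 140 g to 7 × 30 = 210 g | 20-30 g |

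The Section 2 row assumes 20 g per unit, as in Table 3 and both examples in 7.2. Table 3's upper day is 40 - 30 = 10 g above the top of the 7.2 range. Two of the named shakes also give 2 × 350 = 700 calories, twice the 7.2 upper limit of 350. Two bars give 2 × 150 = 300 calories, which is within it. So the protein excess applies to both example products, and the calorie excess and the 12.2 limit apply to the shake.

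**Step 2. Can Table 3's 4 days be a minimum?** The exercise row of Table 3 also says 4 days a week, and Section 7.1 gives that target as "at least 30 minutes per day for 4 or more days per week". Section 12.4 uses at least 4 days for both exercise and protein. The reading is plausible, though the nutrition row does not state it. It removes 7 days against 4 and leaves 1 against 1-2 units a day.

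**Step 3. The 8.2 ratio.** Adherence = units consumed ÷ units provided. For a participant who takes 4 units a week:

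| Assumed supply rule | Adherence |
|---|---|
| 4 a week (Table 3, lower) | 4/4 = 100% |
| 7 a week (Section 2) | 4/7 = 57% |
| 8 a week (Table 3, upper) | 4/8 = 50% |

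**Step 4. Two ways the denominator can grow without any change in intake.** Both examples rest on assumed shipments.

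- Surplus: a participant takes one unit daily for 21 days. With 21 units provided the score is 21/21 = 100%. With 7 spare units (28 provided) it is 21/28 = 75%.
- Switch under 12.2: 28 shakes are provided for a 28-day program, the participant changes to bars after day 7, and 21 bars are then sent. Intake is 7 + 21 = 28 and provision is 28 + 21 = 49, so the score is 28/49 = 57% despite a unit every day.

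**Step 5. Prescribed units as denominator (one a day over own program days).** Daily use scores 21/21 = 28/28 = 100%, including the switch case. Four a week scores 12/21 = 16/28 = 57% at either program length. Eight a week would give 8/7 = 114%, so a cap is needed to stay within the stated range.

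**The case against.** The best case on the other side is that the documents settle more of this than the conflicting wording suggests.

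- *Supply is linked to a dose.* Section 2 says that the one-a-day supplement is the one the study supplies, and Section 7.2 says purchasing is done per participant. If each person gets one unit per day of their own program, the existing ratio gives the same 100% and 57% as the prescribed-unit ratio. This stands in part. A reader might infer that supply is tied to no dose at all, and that goes too far. But the wording in 7.2 sets a sufficiency and not a count, and nothing says how unused shakes are treated after a switch.
- *No bias by program length is shown.* A reader might take the 75% result as evidence that short programs score lower. It needs a uniform 28-unit shipment, which the documents do not describe and the per-participant wording does not suggest. It is an illustration only.
- *The shake limit governs.* Section 12.2 is a specific instruction and Table 3 a general goal, so a careful reader would follow 12.2. That is fair: nothing tells shake users to take two. Table 3 still states a goal that these users may not reach, and 40 g exceeds 7.2 for bars as well.
- *Kidney disease.* A reader might infer a separate defect, a ratio of 0/0 for participants with CKD stage 3 or higher. Table 3 and Section 7.2 already take them out of this component, so 8.2 only fails to repeat the exclusion.
- *Low stakes.* Section 11.1 plans no statistical testing, and change in protein intake by 3-day recall is measured independently of supply. This stands and limits the weight of the point.

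**Conclusion.** The dose conflict holds on the current text. One unit a day and one to two units a day are different instructions, and the upper goal of 40 g is outside 7.2 for the example products and outside 12.2 for shake users. This needs no assumption beyond the 20 g unit that Table 3 itself states.

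The denominator point holds in a smaller form. The 8.2 ratio can be computed, and it is sound if exactly one unit per program day is provided and nothing is replaced. Because the count is not fixed, surplus or replacement product can lower the score with no change in behavior. The actual size cannot be known from the documents; the 57% and 75% figures depend on the shipments assumed above.

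The reach is limited to what participants are told to take and to one descriptive, self-reported secondary outcome. The primary outcome counts sessions delivered, and the protein criterion in 12.4 counts days per week, so neither uses supplement units. The correction is worth making before the dose is carried into the RCT, but it does not threaten the pilot's main conclusion.

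**What to change.** 1. In Table 3, replace the nutrition goal with one supplement per day (20-30 g protein, as in 7.2). State that 4 days a week is the minimum adherence target used in 12.4.
2. In 8.2, define protein adherence as units consumed divided by units prescribed (one per day) over the participant's own 21-28 program days, capped at 100%. Limit it to participants prescribed the supplement, which carries the existing CKD exclusion into the outcome definition.

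The cost is wording in Table 3 and 8.2. Sections 2, 7.2 and 12.2 already fit one supplement a day. The number of supplements consumed is already a Table 3 measure, and 8.2 already uses program days for exercise and meditation, so no new data, visits or participants are needed. The small downside is that the reported percentage may move either way: from 100% to 57% if 4 a week would have been both supplied and taken, or from 75% to 100% in the surplus illustration.
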